4.4 Sample size calculation

We carefully determined the required number of patients to ensure reliable outcome estimates in collaboration with co-creating stakeholders and by consulting orthopaedic surgeons using an online survey on what constitutes convincing evidence. The agreed sample size is 250 patients per group. Therefore, we plan to randomize 250 patients per study group resulting in a total of 750 THA and 750 TKA patients.

To provide a rough indication of the statistical power, we used the online power calculator tool available on Sealed Envelope [20]. The sample size calculation is based on the comparison of RFU vs. active COD as the primary analysis. For this calculation, we assumed that the actual complication rate in both groups is 10%. With the agreed number, it is possible to detect a clinical relevant difference of 10% in complications between the two groups. If there is truly no difference between active COD and RFU, 190 patients per group are needed to be 80% sure that the limits of a two-sided 95% confidence interval will exclude a difference between active COD and RFU of more than 10%. Anticipating 20-25% loss to follow up, we plan to randomize 250 patients.

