10.1 Primary study parameter(s)

The total number of complications at 1 year follow-up (11 years after surgery) and process evaluation expressed by the health care consumption, like the number of clinical visits and X-rays, will be presented by median and interquartile range. For the primary aim, the number of complications will be compared between 2 groups, namely the RFU and active COD, using generalized linear mixed models (GLMM), with a Poisson distribution. A random intercept for centre will be included in the model to account for clustering of patients within centres and a main effect for group is added to determine treatment effect. We will also determine adjusted intervention effects, by accounting for relevant baseline characteristics such as age, gender, BMI, ASA-score, ethnicity, employment status, home-hospital distance and educational level.

The type of complications at 1 year follow-up (11 years after surgery) will be presented categorically by numbers and percentages. The type of complications will be compared between 2 groups (RFU vs. active COD) using GLMM with a logistic regression approach, including a main effect for group, a random intercept for centre and adjusting for baseline characteristics such as age, gender, BMI, ASA-score, ethnicity, employment status, home-hospital distance and educational level.

Process evaluation outcomes will also be expressed dichotomously (i.e. clinical visit: yes/no, X-ray: yes/no etc.) and analysed using logistic GLMM.

The primary outcomes are based on intention-to-treat analyses.

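### The trial is sized for equivalence on a risk difference (±10 points), but the primary analysis is a Poisson comparison of counts with no margin or confidence-interval rule

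*Protocol*

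**What the plan says.** **Sizing (Protocol 4.4).** The calculation is tied to one comparison: "The sample size calculation is based on the comparison of RFU vs. active COD as the primary analysis". Its input is a proportion: "we assumed that the actual complication rate in both groups is 10" per cent. Its criterion is an interval that must stay inside a limit: "190 patients per group are needed to be 80% sure that the limits of a two-sided 95% confidence interval will exclude a difference" larger than 10% between the arms. After allowing for loss, 250 per group are randomised, for THA and TKA each: "Anticipating 20-25% loss to follow up, we plan to randomize 250 patients".

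The same section also describes the agreed number as enough to detect a 10% difference, which is the language of a superiority test. The calculator in its reference (Protocol 14, reference 20) is for a continuous-outcome non-inferiority trial.

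**Analysis (Protocol 10.1).** For the primary aim, "the number of complications will be compared between 2 groups, namely the RFU and active COD, using generalized linear mixed models" with a Poisson distribution, a random intercept for centre and a main effect for group. Logistic models are planned for type of complication and for the dichotomised process outcomes. None is planned for having any complication, yes or no. Section 10 gives no margin, no risk difference and no rule for concluding that COD may replace RFU.

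**Expected conclusion (Protocol 1).** The sponsor expects that COD can safely take the place of RFU at 10 years.

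**The concern.** Three things change between section 4.4 and section 10.1:

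| | Section 4.4 | Section 10.1 |
|---|---|---|
| Endpoint form | proportion of patients with a complication | number of complications |
| Scale | absolute difference in risk | rate ratio (usual log link) |
| Decision | 95% limits exclude more than 10 points | none stated; a group effect is estimated |

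Section 10.1 is not a detail left for a statistical analysis plan. The protocol fixes a primary model, and that model is not the one the trial was sized for. The 80% assurance is therefore attached to an analysis that is not planned.

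The expected conclusion is that omitting the visit does no harm. A group effect that is not statistically significant does not show this. An interval judged against a margin does. With neither a scale nor a rule in section 10, both could be chosen after the results are known.

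**Working it through.** **Inputs.** Risk 10% in both arms, margin 10 points, two-sided 95% interval, 80% power, 190 per group, 250 randomised, 20-25% loss (all Protocol 4.4). z(0.975) = 1.960, z(0.90) = 1.282, z(0.80) = 0.842. Steps 2 to 4 assume no overdispersion and no centre effect.

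**1. Reproduce the plan's figure.** Equivalence on a risk difference, both limits inside ±10 points, true difference zero:

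n = 2p(1−p)(z(0.975) + z(0.90))² / d² = 2 × 0.1 × 0.9 × (3.242)² / 0.1² = 189.1, so 190. This matches.

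Other readings do not match:
- Non-inferiority, one-sided 2.5%: 2 × 0.1 × 0.9 × (1.960 + 0.842)² / 0.1² = 141.3, so 142.
- Superiority, 10% v 20%: 197 or 199, depending on the variance formula.
- Equivalence with a 90% interval: 155.

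**2. Same margin, Poisson rate difference.** The variance is p, not p(1−p), per patient.

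SE = √(2 × 0.1 / 190) = 0.0324

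Power = 2Φ(0.1/0.0324 − 1.960) − 1 = 2Φ(1.12) − 1 = 0.74. A simulation of 400,000 trials gave 73-76%.

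For 80%: 2 × 0.1 × (3.242)² / 0.1² = 210.1, so 211 evaluable per arm. With an assumed overdispersion factor of 1.5, power at 190 falls to about 42%.

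**3. Rate-ratio scale.** The protocol gives no ratio margin. Assume that 10 points on a 10% base is a ratio of 2.0. Expected events are 190 × 0.10 = 19 per arm.

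SE(log ratio) = √(2/19) = 0.324, so the 95% interval is the estimate times or divided by exp(1.96 × 0.324) = 1.89.

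P(upper limit < 2.0 | equal rates) = Φ(ln 2/0.324 − 1.960) = Φ(0.18) = 0.57.

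**4. A plain test of no difference.** With a true doubling, expected events are 19 and 38.

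SE = √(1/19 + 1/38) = 0.281

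P(significant) = Φ(0.693/0.281 − 1.960) = Φ(0.51) = 0.69. About 31% of trials are non-significant (29% by simulation).

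**5. If non-inferiority is what is meant (one-sided 2.5%, 190 per arm).** Risk difference: Φ(0.1/0.0308 − 1.960) = 0.90, with SE = √(2 × 0.1 × 0.9 / 190) = 0.0308. Rate difference: Φ(1.12) = 0.87.

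**6. Loss to follow-up.** 250 × 0.80 = 200 and 250 × 0.75 = 187.5. For 190 to remain, loss may be at most 1 − 190/250 = 24%; at 25% loss, 190/0.75 = 253.3, so 254 would be needed. Equivalence power on the risk difference at 187 is 2Φ(0.1/0.0310 − 1.960) − 1 = 0.79.

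**The case against.** The margin is not absent from the protocol. Section 4.4 states the 10% limit, the two-sided 95% interval and the comparison it applies to, and calls its power figure only a rough indication. A risk or rate difference could be derived from a fitted model and held to ±10 points. On any complication, the risk difference keeps 80% at 190 evaluable. On a Poisson rate difference the loss is from 80% to 74%, and under non-inferiority the power is above 80% on either difference scale. Section 10.1 names no p-value, so that a non-significant result would be read as safety is a possibility and not a stated plan. All of this stands. It limits the point to a mismatch that can be repaired, but does not remove it: nothing in section 10 says that such a difference will be derived or judged.

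The loss figure is also minor. Complications and revisions can come from the patient record and the arthroplasty register, so missing questionnaires need not mean a missing endpoint.

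A reader might infer more than the documents support:
- *That the trial cannot show replacement is safe.* This holds only for a group-effect test taken alone.
- *That power is far lower because the ratio must lie within 0.5 to 2.0.* On a 10% base, a ratio of 0.5 is a 5-point reduction, not the 10 points of section 4.4.
- *That a likely non-significant result at a ratio of 1.5 shows the danger.* That is 10% v 15%, inside the 10-point margin.
- *That visits requested under COD dilute the comparison.* They are the intervention as defined; only missed routine visits are non-adherence.
- *That a per-protocol analysis is wrongly excluded.* The text says "The primary outcomes are based on intention-to-treat analyses", which rules out no supportive analysis, and such sets commonly belong to the statistical analysis plan. Summarising counts by median and interquartile range is a matter of presentation.

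**Conclusion.** The point holds in this form. Section 4.4 sizes a binary equivalence comparison on a risk difference. Section 10.1 specifies a Poisson model for counts, and section 10 has no margin or interval rule. The 80% belongs to the first and not to the second.

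At 190 evaluable per arm, power is about 74% for a Poisson rate difference held to ±10 points. That is the like-for-like comparison. The 57% on the ratio scale depends on reading 10 points as a ratio of 2.0, which the protocol does not say. A plain test of no difference would miss a true doubling in about 30% of trials. These figures rest on the protocol's 10% rate; overdispersion would lower them.

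Which hypothesis is intended is unsettled. The arithmetic is equivalence, one sentence speaks of detecting a difference, and the cited tool is for non-inferiority with a continuous outcome. The sponsor has to decide this first. The 25% loss figure is a small but genuine slip (187 evaluable, about 79% power).

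**What to change.** **In section 10.1:**
- State the hypothesis: equivalence as sized, or non-inferiority if that is what is meant.
- Make the primary clinical estimate the risk difference (active COD minus RFU) in patients with at least one complication by 12 months, with its two-sided 95% confidence interval, for example by standardisation from a logistic GLMM with centre as random intercept.
- State the conclusion rule against the 10-point margin of section 4.4, separately for THA and TKA. Under equivalence, the whole interval lies within ±10 points. Under non-inferiority, the upper limit lies below +10 points.
- Keep the Poisson rate ratio as a secondary analysis.

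Alternatively, keep the rate model as primary, give it a scale, margin and rule, and restate the power in section 4.4 for it (about 74% at 190 evaluable for a rate difference held to ±10 points, or 211 evaluable for 80%).

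**In section 4.4:** name the calculation as binary-outcome, correct the calculator citation, drop or reconcile the wording about detecting a difference, and give either the power as about 79% at 25% loss or the loss as up to 24%.

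**Cost.** The first route needs an amendment of wording only, with no new data or patients. The quoted power at 25% loss becomes slightly less favourable. The second route means accepting a lower stated power or recruiting more. Either should be settled before outcome data are seen.

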8. METHODS

8.1 Study parameters/endpoints

8.1.1 Main study parameter/endpoint

Clinical endpoint:

- Number and type of complications
Described as unplanned, unexpected and undesired outcomes related to THA or TKA that are directly associated with the care or services provided to the patient (i.e. knee- or hip related complaints or changes on X-ray that lead to extra FU, a referral to another specialism or (surgical) intervention) (like infection, peri-prosthetic fracture, loosening, malalignment or malposition of components, prosthetic wear, dislocation, etc)

Process endpoint:

- Healthcare consumption related to THA and TKA FU (number of X-rays and clinical visits)

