10. STATISTICAL ANALYSIS

All analyses will be performed separately for THA and TKA and will be performed using IBM SPSS statistics (SPSS software version 28.0) or R. Categorical data will be presented as numbers and percentages. Continuous variables will be presented by mean and standard deviation in case of a normal distribution. In case of non-normality, median and interquartile range will be given.

Mixed models are used to deal with missing data; when necessary and possible we will perform multiple imputation.

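### The only between-group comparison of complication type is a logistic GLMM adjusted for eight or more covariates, on about 5 to 8 expected events per type; adjusted estimates would be overfitted and very imprecise

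*Protocol*

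**What the plan says.** - Section 8.1.1 gives the main clinical endpoint as "Number and type of complications". It illustrates type by a list ("like infection, peri-prosthetic fracture, loosening, malalignment or malposition of components, prosthetic wear, dislocation, etc").
- Section 10.1 first reports types descriptively, as counts and percentages. It then compares RFU with active COD by a logistic GLMM with a group effect and a random centre intercept, "adjusting for baseline characteristics such as age, gender, BMI, ASA-score, ethnicity, employment status, home-hospital distance and educational level".
- For the number of complications, section 10.1 specifies a Poisson GLMM with a group effect and adds the covariate-adjusted effect as a further analysis. For type, no unadjusted comparison is given alongside the adjusted one.
- Section 10: "All analyses will be performed separately for THA and TKA".
- Section 4.4: "we assumed that the actual complication rate in both groups is 10" per cent. It gives no rate by type.
- Section 10.2 repeats the number and type analyses over three groups. It uses the same kind of adjusted logistic GLMM for type of surgical intervention.

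**The concern.** A logistic model is limited by its number of events, not its number of patients. Splitting the complications first by joint and then by type leaves each model with a handful of events. Against these the plan sets a group effect, at least eight covariate terms and a centre variance over ten hospitals. ASA score, ethnicity, employment and education will probably need several terms each.

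With so few events, some covariate levels will contain none. Their coefficients then have no finite maximum-likelihood estimate, and software reports non-convergence or arbitrary large values. The treatment coefficient is estimated in the same overfitted model. The introduction's stated worry is missed complications with serious consequences. If these fall into rare types, they are where the model behaves worst.

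**Working it through.** **1. The plan's own sample size.** Inputs from section 4.4: rate p = 0.10 in both arms, limit d = 0.10, two-sided 95% interval, 80% power with both limits to exclude d.

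n = 2p(1 − p)(z₀.₉₇₅ + z₀.₉₀)² / d² = 0.18 × (1.960 + 1.282)² / 0.01 = 189.1, so 190 per group. The stated 190 reproduces. The 250 randomized leave 250 × 0.80 = 200 or 250 × 0.75 = 187.5 after the anticipated loss.

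**2. Events per joint.** RFU plus active COD, one joint:
- evaluable: 2 × 190 × 0.10 = 38
- randomized: 2 × 250 × 0.10 = 50

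**3. Events per type.** Six types are named, and a remainder category makes seven. Assuming an even split and one type per complication:
- 38/7 = 5.4 and 38/6 = 6.3
- 50/7 = 7.1 and 50/6 = 8.3

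**4. Events per slope.** Group plus eight one-term covariates is 9 slopes. With multi-level coding of ASA, ethnicity, employment and education it is about 14.
- 9 slopes: 5.4/9 = 0.6 to 8.3/9 = 0.9
- 14 slopes: 5.4/14 = 0.4 to 8.3/14 = 0.6

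The intercept and centre variance come on top.

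**5. What such fits do.** Logistic data were simulated with no true effects, 300 data sets per setting. A linear-programming check looked for separation in any coefficient, complete separation, and an infinite group coefficient. Category frequencies were assumed. For example, in the one-term coding, the less common level of ethnicity had 10% and of employment 15%. The random centre intercept was left out.

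| Covariate terms | Patients, events | Some coefficient infinite | Group coefficient infinite | Median SE of group log-OR | 95% CI: OR divided and multiplied by |
|---|---|---|---|---|---|
| 8 | 380, 5 | 87% | 7% | 0.98 | 6.8 |
| 8 | 380, 6 | 79% | 5% | 0.90 | 5.8 |
| 8 | 500, 7 | 74% | 1% | 0.81 | 4.9 |
| 8 | 500, 8 | 66% | 0% | 0.76 | 4.4 |
| 13 | 380, 5 | 100% | 8% | 1.04 | 7.7 |
| 13 | 380, 6 | 100% | 3% | 0.95 | 6.4 |
| 13 | 500, 7 | 99.7% | 2% | 0.86 | 5.4 |
| 13 | 500, 8 | 99.7% | 1% | 0.77 | 4.6 |

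Complete separation did not occur at 5 to 8 events. At 3 events the group coefficient was infinite in 29% to 31%.

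**6. How much is due to adjustment.** A group-only model has an infinite group estimate only if all e events fall in one arm, with probability 2 × 0.5^e: 6.3% at 5 events, 3.1% at 6, 1.6% at 7, 0.8% at 8. The covariates hardly change that rate.

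In a second run (1,000 data sets per setting, same assumptions, both arms with events), adjustment raised the median SE at 5 events from 0.92 to 0.98 (8 terms) or 1.05 (13 terms). The median shift in the group log-OR was 0.07 to 0.19 over all settings. At 5 events the OR moved by more than 1.5-fold in 8% (8 terms) to 21% (13 terms) of data sets; other assumed codings gave up to about a quarter.

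**The case against.** A reader might infer that most of these models return no usable treatment estimate, or that adjusted type-level odds ratios cannot be estimated at all. The documents do not support that. The separation is partial and sits almost always in a sparse covariate level. The RFU versus active COD coefficient stays finite in about 92% or more of data sets at 5 to 8 events. Most of its imprecision comes from the event count and would remain in an unadjusted interval.

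Four further points can be made for the plan:
- **Counts are already reported by type.** This stands. Readers will see the raw numbers beside any model, which limits the harm. But counts carry no contrast or interval, and the one contrast specified is the fragile one.
- **The inputs are open.** The list of types is illustrative, and the covariate list is given as examples. Types will not split evenly, so a common type may be adequately served: at 15 events the SE falls to about 0.55. This stands as a limit on the figures. It does not rescue the rarer types.
- **Covariate coding, grouping of types and handling of non-convergence are usually left to the SAP, which is not at hand.** True, and their absence is not the point. The protocol itself names the adjusted model as the type comparison.
- **The primary aim is carried by the number of complications.** Section 4.4 sizes the trial on the overall rate ("190 patients per group are needed to be 80% sure that the limits of a two-sided 95% confidence interval will exclude a difference" beyond the limit), and no power claim attaches to single types. This bounds the importance of the point.

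**Conclusion.** The point holds as a badly fixed analysis choice for part of the main clinical endpoint. At the plan's own rate, the adjusted GLMM would work with less than one event per slope for a typical type. Most fits would show separation in at least one covariate level, with convergence problems. The treatment estimate would usually be finite, but overfitted and very imprecise (SE about 0.75 to 1.05). Randomization already guards against systematic confounding between these two arms, so the adjustment offers little in return.

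The event count rests on the 10% rate, one type per complication and an even split over six or seven types. The separation rates rest also on assumed covariate codings and frequencies. The comparison of the total number of complications is not affected by this point.

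**What to change.** In section 10.1, keep the counts and percentages per arm. Make the type-level comparison an unadjusted risk difference with an exact 95% confidence interval, or a penalised (Firth-type) logistic model with group only. Fit the covariate-adjusted GLMM only for types above an event count fixed in advance. Set that count together with the covariate coding: at 15 events, 29% of simulated fits still separated with 8 covariate terms and 97% with 13.

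Apply the same rule in section 10.2 to the three-group analysis of complication type and to type of surgical intervention. Leave the adjusted analysis of the total number of complications as it is.

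The change is to analysis wording and needs no extra patients or data. The small cost is that rare types get no adjusted odds ratio and no centre effect.

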Intervention: COD (intervention): no follow-up visit 10 years after THA or TKA but only check-ups requested by both the health care professional (HCP) or the patient. The intervention group will be split into two groups: one group will be informed about the study and will fill out questionnaires (active COD), one group will not be contacted to avoid any trigger to contact a HCP (passive COD). RFU (control): follow-up visit 10 years after THA or TKA combined with questionnaires.

Main study parameters/endpoints: primary outcomes: complications (clinical outcome), healthcare consumption (process outcome); secondary outcomes: PROMIS physical function, surgical interventions, NRS pain, NRS satisfaction, EQ-5D-5L, and costs for healthcare and societal perspectives.

Nature and extent of the burden and risks associated with participation, benefit and group relatedness: No additional risks are expected compared to standard care, as both RFU and COD 10 years after THA or TKA are part of current clinical practice. Patients are required to spend time completing questionnaires. Only the RFU group will be asked to visit the hospital.

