2. OBJECTIVES

Primary Objective: Investigate the (cost-)effectiveness of replacing RFU after THA and TKA at 10 years by COD by comparing complications and clinical visits between patients with COD versus RFU at 10 years after THA and TKA, after a follow-up of 1 year.

Secondary Objective(s): Investigate the effect of COD compared to RFU at 10 years after THA and TKA on surgical interventions, physical function, quality of life, pain and costs , after a follow-up of 1 year.

Investigate the effect of informing patients about COD on complications, clinical visits, surgical interventions, and costs.

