In case of a clinical visit information will be collected about the visits, like whether the visit was a routine visit or on demand, the reason for the visit, date of the visit, consequences of possible findings (like change in policy and secondary health consumption). In case of a routine visit, we will collect data whether the patient cancelled the appointment and the reason of cancellation.

PROMIS physical function will be obtained using the short form (SF) [22]. In case hospitals already use computer adaptive testing (CAT) of PROMIS physical function in clinical practice, this will be used. Version 10b will be used. The SF PROMIS physical function consists of 10 questions and is expressed by raw summed score ranging from 10 to 50, which can be converted to a T-score and SE. The T-score is a standardized score with a mean of 50 and a SD of 10.

EuroQol-5D (EQ-5D-5L) is a general health-related quality of life questionnaire and consists of five questions regarding mobility, self-care, usual activities, pain/discomfort and anxiety/depression and one visual analog scale (VAS) to document the perceived quality of life [23]. The quality of life is described by 2 scores, the index value, which range from 0 to 1, and the VAS score, which range from 0 to 100. For both scores applies the higher the better. Numeric Rating Scale for pain (NPRS) is a scale ranging from zero to ten on which patients can score their pain [24]. It is a widely used instrument in varying populations due to its ease of administration and clinical relevance to the patient. The lower the score, the better.

Numeric Rating Scale for satisfaction (NSRS) will be measured by a single question: "How satisfied are you with the results of the treatment?" The patient will answer this question with a NRS scale ranging from zero to ten. The higher the score, the better.

Health consumption and costs will be measured using the EPD. Health consumption includes both the primary outcomes clinical visits and X-rays, as well as additional health care use, including telephone consultations and scans. The LROI register will be used to collect data about revision surgery. A questionnaire will be used to get more insight in the health consumption and costs which cannot be obtained from the EPD. This questionnaire is made in collaboration with a HTA expert and patient representatives.

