10.2 Secondary study parameter(s)

For the secondary analysis, the aforementioned GLMM analyses on number and type of complications and clinical visits will be repeated comparing the 3 groups, namely the RFU, active COD and passive COD.

Secondary patient-reported outcomes, namely PROMIS physical function, NPRS, NSRS and EQ-5D-5L, will be presented as mean with standard deviation in case of normality or median and interquartile range otherwise. These parameters will be analysed using linear mixed models, with repeated measures clustered within participants and participants within

hospitals (random intercepts). Intervention group (RFU vs. active COD vs. passive COD), baseline score, and time (3, 6, 12 months) are included as fixed effects, to determine the crude effect of the intervention. To correct for possible confounders, baseline variables will be added to the model as fixed effects.

The total number of surgical interventions at 1 year follow-up (11 years after surgery) will be presented by median and interquartile range. The number of complications will be compared between 3 groups, namely the RFU, active COD and passive COD, using GLMM, with a Poisson distribution. A random intercept for the centre will be included in the model to account for clustering within centres. GLMM will also be used to correct for and to investigate the effect of possible confounders..

The type of surgical interventions at 1 year follow-up (11 years after surgery) will be presented categorically by numbers and percentages. The type of surgical interventions will be compared between 3 groups using GLMM with logistic regression, adjusting for possible confounders and incorporating centre as a random intercept.

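### The primary process endpoint is a count of visits and X-rays, but section 10.1 states no between-group model for the counts, only a logistic model on any visit or X-ray, which does not track net visits saved

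*Protocol*

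**What the plan says.** The primary objective in section 2 includes "comparing complications and clinical visits between patients with COD versus RFU at 10 years after THA and TKA". Section 8.1.1 defines the process endpoint as a count: "Healthcare consumption related to THA and TKA FU (number of X-rays and clinical visits".

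Section 10.1 handles this endpoint in three places:
- The counts are described only: "process evaluation expressed by the health care consumption, like the number of clinical visits and X-rays, will be presented by median and interquartile range".
- The Poisson GLMM with a random centre intercept is tied to complications: "For the primary aim, the number of complications will be compared between 2 groups, namely the RFU and active COD".
- A model for process outcomes is named once: "Process evaluation outcomes will also be expressed dichotomously (i.e. clinical visit: yes/no, X-ray: yes/no etc.) and analysed using logistic GLMM".

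Section 10.2 then refers back: "the aforementioned GLMM analyses on number and type of complications and clinical visits will be repeated comparing the 3 groups". Section 10.4 extends the same GLMMs with interaction terms, for clinical visits and X-rays as well as complications.

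On the intervention, the Summary states "RFU (control): follow-up visit 10 years after THA or TKA combined with questionnaires". Table 1 restricts the scheduled baseline visit and X-ray to the RFU group. Section 8.3 also foresees cancelled routine appointments and records, for each visit, "whether the visit was a routine visit or on demand".

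**The concern.** The process question is whether COD lowers total use once on-demand visits under COD and follow-on visits after RFU are both counted. That calls for a comparison of counts. The only between-group comparison stated is of any visit or any X-ray, and nothing in 10.1 sets aside the appointment that defines the RFU arm. A yes in RFU is then largely produced by allocation, while a COD patient with one on-demand visit scores the same as one with four.

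At stake is half of the primary objective. The text, followed as written, would report a very large and highly significant odds ratio under any plausible result, and the size of the net saving would not appear in the primary process analysis.

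**Working it through.** **The plan's own figure.** The protocol gives no sample size, power or expected rate for the process endpoint. Section 4.4 gives 190 evaluable patients per group for complications (10% in both groups, both limits of a two-sided 95% CI within 10 points, 80% power). This reproduces: 2 × 0.10 × 0.90 × (1.960 + 1.282)² / 0.10² = 189.1, so 190. It serves below only as the number per arm for one joint.

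**Assumptions (none is in the protocol).** RFU attendance a = 0.95. Further visits per RFU patient are Poisson with mean 0.1. The share of COD patients with any visit is p = 0.30. Each such patient makes m visits on average, as 1 + Poisson(m − 1), with m from 1 to 4.

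**Odds ratio for any visit.**
- RFU, any visit: 1 − 0.05 × e^(−0.1) = 0.955, odds 21.1.
- COD, any visit: 0.30, odds 0.429.
- Odds ratio, COD v RFU: 0.429 / 21.1 = 0.020. It does not involve m.

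**Mean visits per patient.** RFU: 0.95 + 0.10 = 1.05. COD: 0.30 × m. Variances: RFU 0.95 × 0.05 + 0.10 = 0.1475; COD 0.30 × (m − 1 + m²) − (0.30m)². SE of the difference: √(sum of the variances / 190).

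| m | COD mean | COD − RFU (SE) | Rate ratio | Odds ratio | Medians, RFU v COD |
|---|---|---|---|---|---|
| 1 | 0.30 | −0.75 (0.04) | 0.29 | 0.02 | 1 v 0 |
| 2 | 0.60 | −0.45 (0.08) | 0.57 | 0.02 | 1 v 0 |
| 3 | 0.90 | −0.15 (0.12) | 0.86 | 0.02 | 1 v 0 |
| 4 | 1.20 | +0.15 (0.15) | 1.14 | 0.02 | 1 v 0 |

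Simulation at 190 per arm agreed to within 0.01. The saving disappears at m = 1.05 / 0.30 = 3.5.

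**Is the yes/no result in doubt beforehand?** The closest case examined, 90% v 50%, gives a difference of 0.40 with SE √((0.09 + 0.25) / 190) = 0.042, more than 9 standard errors. Power is about 100% throughout 90–98% attendance against 10–50% in COD.

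**Dependence on attendance, COD unchanged (p = 0.30, m = 2).**
- a = 0.85: any visit in RFU 1 − 0.15 × 0.905 = 0.864; odds ratio 0.067; rate ratio 0.60 / 0.95 = 0.63.
- a = 0.98: any visit in RFU 1 − 0.02 × 0.905 = 0.982; odds ratio 0.008; rate ratio 0.60 / 1.08 = 0.56.

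The odds ratio shifts more than eightfold; the visit rate ratio barely moves.

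**Separation.** If every analysed RFU patient is a yes, the logistic model has no finite estimate. Taking attendance as the chance of a yes, the probability is aⁿ:

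| Attendance | n = 190 | n = 250 |
|---|---|---|
| 95% | 0.01% | <0.01% |
| 98% | 2.2% | 0.6% |
| 99% | 14.8% | 8.1% |
| 99.5% | 38.6% | 28.6% |

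In a subgroup cell of 10 RFU patients at 95% attendance it is 0.95¹⁰ = 60%.

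**The case against.** **A count model seems to have been meant.** The endpoint is a number, the word *also* marks the yes/no form as an addition, and 10.2 and 10.4 refer back to GLMMs for visits. A reader might infer that the sponsor chose a logistic analysis instead of a count analysis; the text does not support that. It is also fair to say that a statistical analysis plan, not shown here, may name the model. What remains is that 10.1 ties the Poisson model to complications and fixes a descriptive summary and a logistic model for visits, and that 10.2 may point to a model that is not there.

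**The logistic model will usually fit.** A reader might infer that it must break down, or could return a non-significant result for the largest contrast in the trial. Cancellations are foreseen and the analysis is by intention to treat, so separation in the main model is negligible at 95% attendance or less and matters only near 99% or above. Small cells in the interaction models of 10.4 are the more realistic exposure.

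**The yes/no contrast carries information.** It is too strong to say that it measures only attendance. The COD proportion is on-demand use, and the contrast shows how many fewer patients have any visit. That is a legitimate supplementary result.

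**The scenarios are chosen.** RFU patients may also contact a professional at any time, and pairing heavy use in COD with light use in RFU is what brings the saving to zero. This stands as a caution about the sign change. The insensitivity runs the other way too. Raising further RFU visits from 0.1 to 0.5 at m = 2 moves the saving from 0.45 to 1.45 − 0.60 = 0.85 visits, yet the odds ratio only goes from 0.020 to 0.013 (RFU odds (1 − 0.05 × e^(−0.5)) / (0.05 × e^(−0.5)) = 32).

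**Net use is partly covered elsewhere.** Additional consumption is a secondary endpoint (8.1.2), and 10.2.1 estimates mean cost differences. The trial is therefore not blind to net use, but a cost difference is not a comparison of the primary process endpoint.

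**Conclusion.** The concern holds as a mismatch between a count endpoint and the analysis stated for it. Section 10.1 names no between-group model for the number of visits or X-rays. Its two stated outputs, the medians and the any-visit odds ratio, would not show net visits saved. Under the assumptions above, an odds ratio of about 0.02 and medians of 1 v 0 are compatible with anything from 0.75 visits saved to 0.15 added per patient. Even without the last scenario, the saving varies fivefold (0.75 to 0.15) with no change in either output.

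This rests on the allocated RFU visit being counted, which 10.1 neither states nor excludes, and on assumed attendance and visit rates. The documents do not show that the sponsor rejected a count analysis or that the main logistic model is likely to fail. The data needed for a sound analysis will be collected.

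**What to change.** In section 10.1:
1. Make the main process analysis a between-group comparison of the number of visits, and of the number of X-rays, per patient. State that the allocated RFU visit and X-ray count. A Poisson or negative binomial GLMM with a random centre intercept, or a mean difference with a robust 95% CI, would serve; report both the rate ratio and the mean difference. Robust standard errors are advisable because dispersion is likely to differ by arm: at m = 3 the assumed RFU variance is 0.15 on a mean of 1.05, and the COD variance is 0.30 × (2 + 9) − 0.90² = 2.49 on a mean of 0.90.
2. Report visits and X-rays beyond the allocated RFU appointment separately, using the routine or on-demand field in section 8.3, and report RFU attendance as adherence.
3. Keep the any-visit and any-X-ray analysis as a supplement only.
4. Align the back-references in 10.2 and 10.4 with the model now named, and base the visit and X-ray interaction models on the counts.

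The cost is protocol or SAP wording and slightly more analysis work, with no new data. The large odds ratio is no longer the headline result.
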